Although a number of prior studies indicate omega-3 fatty acid supplementation is beneficial to pregnancy and a developing fetus, many studies have been inconclusive. Thus, there may be unknown teratogenic effects on a fetus exposed to high levels of omega-3. In order to decrease the risk of harm to females and their fetus if pregnant, pregnancy at any point while enrolled is

exclusionary for this protocol. Urine pregnancy screens at time points throughout study participation are performed to verify a subject's verbal declaration of not being pregnant, or verbal declaration to the contrary. All potential female participants are informed, verbally and through the informed consent document, that pregnancy is exclusionary at all times and that getting pregnant may expose that individual and her fetus to unknown risks. Participants will be reminded of pregnancy exclusion and risks during study visits.

Although there is no known risk to subjects or their fetus if receiving an MRI scan, exposing subjects or their fetus to the high magnetic fields generated by an MRI machine may involve unknown risks. Thus, subjects will not be pregnant at any point in this study.

Any subject who becomes pregnant during participation in a clinical study for which pregnancy is a standard exclusion criterion must be promptly withdrawn from the study. Long-term follow-up information regarding the outcome of the pregnancy and any postnatal sequelae in the infant will be required. We will be monitoring all female subjects for pregnancy each month. Subjects receiving an MRI will receive a urine pregnancy before receiving a scan.

The effects of the drugs on the male reproduction are not entirely known. Therefore, male subjects should not cause a pregnancy. If a male subject causes a pregnancy during this study, long-term follow-up information regarding the outcome of the pregnancy and any postnatal sequelae in the infant may be required.

Since this study involves subjects that use an illegal substance, cannabis, and since this study involves subjects whose risk of using other illegal substances is high, there is a risk that subjects may be incarcerated while enrolled in this protocol. In the event that a currently enrolled subject is incarcerated, the University of Cincinnati Medical Center Institutional Review Board will be informed and, either the subject will be removed from the study if the PI determines that the study medicines and therapy are not tolerated or efficacious, or permission will be requested of the IRB to allow for the inclusion of prisoners and the subject will continue study treatment until follow-up care can be arranged.

As with any study, there is a potential risk of loss of confidentiality, although every attempt will be made to ensure confidentiality, unless mandated by the law or a situation where an adolescent or parent is a danger to him- or herself or others as described below. The coding of subjects immediately following provision of informed consent/assent to mask their name and identifying information minimizes this risk. All information on subjects will be stored in binders with subject codes only and these binders will be kept in a locked cabinet. In addition, all information on subjects will be stored with subject codes only on computer databases in which access is limited to research personnel. All publications resulting from the study will be presented as group data; no identifying information will be used. In the event of data sharing all subject information will be de-identified. Consistent with the Federal guidelines, participants will be informed of the federally mandated reporting laws for child abuse and neglect, verbally and in the written consent form. Therefore, if abuse or neglect is suspected the Department of Human Services will be called. Risks associated with this include embarrassment, legal consequences, and removal of the child from the legal guardians' home. Subjects will be informed during the consenting procedure that if, at any time, they or their legal guardians decide to terminate study participation, they will be given a referral for further treatment as indicated. Additionally, if the study physician determined it is unwise for the subject to continue in the study because of ineffectiveness or intolerable side effects of the study medication, their participation will be stopped. Patients who are discontinued from the study for any reason will be given a referral for further treatment as indicated.

There are no human risks known to undergoing an MRI. The risk of feeling claustrophobic while in an MRI does exist and subjects will be made aware of this prior to signing consent.

The risks to the participating subjects are reasonable in relation to proposed benefits to mankind. Indeed, the US FDA has mandated the pharmaceutical industry to further clinical studies in the pediatric population in order to provide data on currently available therapies. The information obtained from subjects participating in this protocol will potentially serve to better treat individuals with similar diagnoses and symptoms in the future. Furthermore, information from this study might provide those suffering from mental illness, especially MDD, a more holistic and cost-effective alternative to current treatment options.

H. Payment: Subjects will be reimbursed for participating in each study visit. They will receive

- \$20 for completing screening procedures,
- \$20 for completing baseline assessments,
- \$20 for completing each follow-up visit (pro-rated at \$15 for the visit + \$5 additional for remembering to bring in their pill dairy and bottles for pill counts), and
- \$50 from the proposed study for participation in the week 12 (or termination) MRS scan. It should be noted that, although subjects will undergo a baseline MRS scan for this proposal, subjects will do so concurrently for the BITREC Project 3 study and are thus paid \$50 for that scan though BITREC Project 3.

Payment will be in the form of cash paid firsthand to the subject or check sent via mail to the subject.

I. Subject Costs: There will be no costs incurred by the subjects as a result of participating in this study. However, patients are expected to provide for clinical care that is not part of this research protocol (e.g., hospitalization costs) through standard health care payment procedures. Subjects will also be responsible for acquiring their own omega-3 fatty acids supplements, if they chose to continue such treatment, after study termination.

J. Consent/Assent Forms: See attached.

K. Literature Cited:

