A randomization schedule stratified by presence vs. absence of ADHD, presence vs. absence of concomitant stimulant treatment (within the ADHD group), and pre-pubescent vs. post pubescent (as determined by the Tanner Questionnaire with scores of 1-2 representing pre-pubescent and scores of 3-5 indicating post-pubescent) will be developed by the on-site biostatistician and will be used to assign omega-3 fatty acids (N=30) or placebo (N=30) treatment in a double-blind manner. We will stratify treatment assignment by some of the independently transmitted variables that contribute to the heterogeneity of at-risk adolescents (i.e. ADHD and concomitant use of stimulants) so that we will be able to assess the effects of these clinical factors on the neurophysiological and omega-3 fatty acid RBC level changes associated with supplementation of omega-3 fatty acids (vs. placebo) and examine potential neurophysiological markers of treatment response within clinically defined subgroups. We selected these variables for stratification because they may each affect outcome and treatment response.

Twelve-week Study Phase: During the 12-week DBPC phase subjects will participate in weekly research visits to assess symptom response and adverse side effects. Following the randomization visit, all visits will be scheduled weekly (or ≤ 10 days apart). The research visits will take approximately 1 hour; at these visits an experienced clinician will evaluate the patients for adverse effects and clinical response. Efficacy assessments will be obtained by a rater who is blind to side effects.

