The ADHD Rating Scale (ADHD Rating Scale-IV),^{46,47} completed by the parent or guardian, will be administered at screening, baseline, and each weekly visit and will be used to assess ADHD symptom severity during the prior week. Rates of ADHD are high in adolescents at risk for developing mania and who have a parent with bipolar disorder.^{6,48} Therefore, excluding these adolescents would limit the generalizability of our findings. Moreover, data suggest that omega-3 fatty acids may be effective for the treatment of ADHD symptoms.⁴⁹⁻⁵² Thus, we will include adolescents with ADHD in our study. However, to be included the adolescent must have been taking a stable dose of psychostimulants during the month prior to baseline.

The Columbia Suicide Severity Rating Scale (C-SSRS)⁵⁶, will be administered by trained raters at each visit as a measure of suicidality. All study investigators and staff have received training from one of the authors of the C-SSRS, [name] at Columbia University. We have incorporated this rating scale into several other studies of adolescents with mood disorders. If any subject experiences worsening of suicidality during the course of the study, they will be discontinued from study participation and receive appropriate clinical care.

The Children's Global Assessment Score (CGAS)⁵⁷ will be administered by a child and adolescent psychiatrist at screening, baseline, weeks 4, 8, and 12 (or termination), and the follow-up visit at week 14, will be used to assess overall function at the time of the rating.

Additionally, psychosocial function during the month prior to baseline will be assessed using the functional rating scales of the Longitudinal Interval Follow-up Evaluation (LIFE).^{58,59} Trained raters with good inter-rater reliability ($\kappa > 0.8$) will evaluate each of four major areas of functioning; role performance, interpersonal relationships, recreational enjoyment, and sexual activity. To assess change in function, the same rater will evaluate each of these four major areas for the prior 4-week period at weeks 4, 8, and 12 (or termination).

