In addition to the clinician rated instruments, for all adolescents ages 9 -18 years and for those adolescents ages 18-21 years, if feasible and permission is obtained from the subject, a primary caregiver will be asked to complete the Child Behavior Checklist (CBCL)⁶⁰ at baseline and weeks 4, 8, and 12 (or termination), and at the week 14 follow-up visit and to rate the period since the prior CBCL (baseline ratings will rate the prior month). If the parent with bipolar disorder is asked to complete the CBCL, we will assess their current mood state by reviewing the mood state module of the SCID. This information will be recorded and controlled for in statistical analyses.

Additionally, for all adolescents who are still in school, a teacher will be asked to complete the Teacher Report Form (TRF)⁶¹ at baseline and week 12 (or termination). We will obtain written permission from the adolescents (if 18-21 years) or their legal guardian (if < 18 years) to contact their teacher and will communicate with the teacher directly to complete the TRF. Using these procedures, we have 96% TRF return rates for our prior studies.

Nutritional Supplement Dosing: Subjects will be randomized to EPA+DHA supplements (omega-3 fatty acids) or placebo (olive oil) provided and encapsulated by the Inflammation Research Foundation. Placebo and omega-3 capsules are identical in size, shape, and color to protect the blind. Capsules will be provided to subjects. The omega-3 fish oil used in these capsules is screened by the International Fish Oil Standards (IFOS) program (www.ifosprogram.com) for PCBs, mercury, heavy metals, and oxidation levels in accordance with Council for Responsible Nutrition's voluntary monograph on omega-3 products and safety standards for human consumption. All capsules will be stored at manufacturer's recommendations (14-24°C), and EPA+DHA content determined upon initial receipt and every 60 d by gas chromatography to assure consistency across the trial. Individual

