group2)/pooled standard deviation. We will use a χ^2 test to compare percent responders (defined by CGI-I ≤ 2) at endpoint between treatment groups.

Prediction 2: Omega-3 fatty acid supplementation will be more effective than placebo for improving behavioral symptoms and psychosocial functioning in adolescents with a high risk for developing mania. A MMRM approach will be used to compare change over time in ADHD-RS scores between treatment groups. Additionally, change over time in CBCL and TRF externalizing and internalizing t-scores will be examined using a MMRM model. We will use a χ^2 test to determine whether the percent of subjects > 18 years old (vs. ≤ 18 year old) with completed CBCL and TRF ratings differs significantly between treatment groups. If there is no statistically significant difference, T-scores for 19-21 year olds will be determined using the gender-specific 18 year old t-scores, since we will be examining for group differences in change in score over time. We will use generalized linear mixed logistic regression models to examine change over time in percent responders (defined by achieving a level of functioning that is equal to or better than the month prior to baseline) in each of the four major areas of functioning; role performance, interpersonal relationships, recreational enjoyment, and sexual activity. A mixed effects model repeated measures (MMRM) approach will be used to compare change over time in CGAS scores between treatment groups. We will also evaluate change from baseline to endpoint in CGAS scores and calculate effect sizes as described. Covariates will be included in these models as described above. Additionally, we will examine the effect of change in mood symptom ratings during a specific time period (YMRS and CDRS-R) on change in behavioral and psychosocial functioning during the same time period by using, a repeated-measures framework in SAS PROC MIXED to account for the fact that multiple observations per individual on the same outcome are correlated across time.

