In order to maximize the safety of the study participants, in addition to adverse event monitoring by study investigators, the proposed study will have a DSMB. The DSMB will consist of non-study related faculty with research related experience and will include a statistician, a psychiatrist with expertise in omega-3 fatty acids, and a child and adolescent psychiatrist. The DSMB members will not have a potential conflict of interest in study related outcomes. The DSMB will meet a minimum of every 6 months during the course of the study and will review tolerability, safety and efficacy data. The DSMB will also review all SAEs at the time of their occurrence and provide recommendations based on this review (e.g., that the study may continue or recommend modifications, including additional tolerability and efficacy measures). Every six months the DSMB will formally review all adverse events as well as all efficacy and tolerability data. Drs. [name] and [name] will be responsible for providing updated efficacy and tolerability data to the DSMB every six months and the independent physician will provide information on group assignment without breaking the blind (e.g. group A and group B). The DSMB will assess the risks and benefits of study participation to all subjects and based on this assessment the DSMB will provide a written report of their analyses and recommendation as to whether the study should continue, modification to the study as needed or if the study should be terminated. [name], in conjunction with the DSMB, will be responsible for making certain that the DSMB files their report to the IRB as well as to the sponsor (NIMH) of the study. The DSMB will also provide the investigator with a summary of their report that will include their recommendations.

In order to maximize subject safety, study participants will be monitored daily by telephone (and in person if needed) during the screening period. Patients will be discontinued from study participation if at any two consecutive visits during the study they have a ≥ 9 point increase in CDRS-R score (1 point increase in $> 50\%$ of the 17 items of the CDRS-R) or ≥ 6 point increase in YMRS score (1 point increase in $> 50\%$ of the 11 items of the YMRS) from baseline. If any of the above occurs, we will refer the patient for treatment in BITREC or the community.

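### A LIFE rating at termination before week 4 looks back a fixed 4 weeks into the pre-baseline reference month, which can only pull a worsened patient toward 'response'; the likely effect is small

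*Combined protocol and SAP*

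**What the plan says.** All references are to the combined protocol and SAP.

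- **Baseline window** (E.a, Assessments, LIFE paragraph): "psychosocial function during the month prior to baseline will be assessed using the functional rating scales".
- **Later windows** (same paragraph): to assess change, the same rater is to "evaluate each of these four major areas for the prior 4-week period at weeks 4, 8, and 12 (or termination". Figure 1 also places LIFE in the week 12 (termination) column. It schedules no LIFE rating between baseline and week 4, and none at week 14.
- **Outcome** (E.b, Prediction 2): response in each of the four areas means "achieving a level of functioning that is equal to or better than the month prior to baseline". The analysis is by "generalized linear mixed logistic regression models to examine change over time in percent responders".
- **Visit spacing** (E.a, Twelve-week Study Phase): "all visits will be scheduled weekly (or ≤ 10 days apart".
- **Routes out before week 4**: under Safety Monitoring, patients are "discontinued from study participation if at any two consecutive visits during the study they have a ≥ 9 point increase in CDRS-R score", with a parallel YMRS limit. The C-SSRS paragraph and Safety Monitoring also discontinue anyone whose suicidality worsens, with no requirement for a second visit.
- **Contrast** (E.a, CBCL paragraph): the caregiver is asked "to rate the period since the prior CBCL (baseline ratings will rate the prior month".

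Nothing in the documents shortens the LIFE window for an early leaver, excludes the rating, or assigns it to a scheduled visit.

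**The concern.** A 4-week look-back suits weeks 4, 8 and 12, where it covers exactly the time since the last rating. It does not suit an unscheduled termination before week 4. There the window must include days from the month that serves as the comparator, so the post-treatment value is partly the baseline value.

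The error runs one way. A patient who is unchanged or improved is a responder whether or not the windows overlap. A patient who has worsened is pulled toward the baseline level, and equality counts as success. For someone who leaves before week 4, the termination rating is the only post-baseline LIFE value, so no later rating corrects it.

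At stake is one Prediction 2 functioning outcome. The CDRS-R and YMRS analyses are not affected.

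**Working it through.** The plan states no figure on this point, so there is none to reproduce.

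**1. Pre-baseline time in the window.** Pre-baseline days = max(0, 28 − day of termination).

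| Visit spacing | Visit 1 | Visit 2 | Visit 3 |
|---|---|---|---|
| 7 days | day 7: 21 days (75%) | day 14: 14 days (50%) | day 21: 7 days (25%) |
| 10 days (maximum) | day 10: 18 days (64%) | day 20: 8 days (29%) | day 30: 0 |

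From day 28 onward the overlap with the baseline month is zero. The suicidality rule can act from visit 1. The CDRS-R/YMRS rule needs two consecutive visits and so can act from visit 2.

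**2. Does overlap change the classification?** Assume an integer scale with higher meaning worse, and a fall in functioning from level 3 to level 4 on day 0. With w weeks since baseline, the window average is 3(1 − w/4) + 4(w/4).

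| Leaves at | Average | Scored by rounded average | Scored by most frequent week | Scored by worst week |
|---|---|---|---|---|
| Week 1 | 3.25 | response | response | non-response |
| Week 2 | 3.50 | depends on rounding | tie | non-response |
| Week 3 | 3.75 | non-response | non-response | non-response |

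If only time since baseline is rated, all three weeks are non-response under every convention.

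**3. Probability of misclassification under averaging.** The assumptions, none of them from the documents, are: latent level uniform on 2 to 4; a full one-level decline from week 1; weekly noise SD 0.2 or 0.5; rating equal to the rounded window mean; 200,000 simulated records per cell. Each entry is the probability of being scored equal or better.

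| Leaves at | SD 0.2: written window / since baseline | Excess | SD 0.5: written window / since baseline | Excess |
|---|---|---|---|---|
| Week 1 | 0.75 / 0.09 | 0.66 | 0.74 / 0.21 | 0.53 |
| Week 2 | 0.50 / 0.07 | 0.43 | 0.50 / 0.17 | 0.33 |
| Week 3 | 0.25 / 0.06 | 0.19 | 0.29 / 0.15 | 0.14 |

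Mean excess: (0.66 + 0.43 + 0.19)/3 = 0.43 and (0.53 + 0.33 + 0.14)/3 = 0.33.

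**4. How many patients?** F.2 (Estimated sample size) allows 25% for dropout and unusable MRS data combined: 0.25 × 60 = 15 at most. The documents do not say how many of these leave early, or when. Assume 8 to 15 leavers spread uniformly over weeks 1 to 11.

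- Leaving before week 4: 8 × 3/11 = 2.2, to 15 × 3/11 = 4.1.
- Extra misclassified per functional area, both arms, if every one of them declines a full level: 0.33 × 2.2 = 0.7, to 0.43 × 4.1, about 1.7.
- Split evenly over two arms of 30: 0.7/60 = 1.2%, to 1.7/60 = 2.8%, or about 1 to 3 points per arm.

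With a half-level decline the average probabilities are 0.73 to 0.75 against 0.50. The excess is 0.23 to 0.25, giving about 0.5 (0.23 × 2.2) to 1.0 (0.25 × 4.1) extra patients.

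**The case against.** The strongest reply is that the overlap matters only under a scoring rule the documents do not give. If LIFE is scored at the worst level in the window, an early decline still shows and nobody is misclassified. This stands, and the consequence has to be stated conditionally. The overlap itself does not depend on the scoring rule.

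A second reply is that equal windows are a reasonable choice, since four weeks matches the one-month baseline period and a one-week rating of role performance or recreation is a weaker comparison. This is a real cost of the fix. But comparability gained by putting pre-treatment time into a post-treatment rating is a poor trade.

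Third, early decline is captured elsewhere. CGAS is rated at termination for function at that moment, and the mood scales are rated weekly for the prior week. This is true and limits the damage, but it does not repair the LIFE analysis.

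Fourth, Prediction 2 does not say how an off-schedule termination rating enters the mixed logistic model. This also stands, so entry as a response is possible but not established.

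A reader might go further and infer that the patients affected are mainly those removed for deterioration. The documents give no breakdown of reasons or timing, and they list other exits, including voluntary withdrawal, side effects, pregnancy and incarceration. The mood rule also cannot normally act at week 1, where the overlap is largest.

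**Conclusion.** The defect is in the text. A fixed 28-day look-back, with no exception, makes a termination rating at week 1, 2 or 3 consist of 75%, 50% or 25% pre-baseline time, and the responder definition lets that time act only toward response.

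The likely effect is small: about 0.7 to 1.7 extra misclassified patients per functional area across both arms, or 1 to 3 points per arm if evenly split. That rests on averaged ratings, 8 to 15 leavers spread uniformly, every leaver before week 4 declining a full level, and the rating entering the model. Under worst-level scoring the effect is nil.

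Three stronger readings are not supported:

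- **A shift of about 7 points in one arm.** This needs two extra misclassified patients in the same arm (2/30 = 6.7%), which is more than the calculation yields for both arms together.
- **Bias toward no difference.** This needs placebo to lose more worsening patients early, which the documents do not indicate. The direction between arms is unknown.
- **The same fault at weeks 5 to 7 and 9 to 11.** Those windows overlap an earlier on-treatment rating but never reach the baseline month.

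This is a worthwhile clarification of a secondary functioning outcome in a pilot trial.

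**What to change.** In the LIFE paragraph, specify the window as: *at weeks 4, 8 and 12, the preceding 4 weeks; at early termination, the time since the previous LIFE rating, or since baseline if before week 4*. This follows the CBCL rule. In Prediction 2, add that no post-baseline LIFE rating may include time before randomisation. With this change the pre-baseline days in the window are zero at every termination time.

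The cost is one sentence in each place and a line in the rater instructions, with no extra visits or staff. The downside is that a termination rating before week 4 rests on 1 to 3 weeks, so it is noisier and matches the one-month baseline window less closely.
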